1. INTRODUCTION

This statistical analysis plan (SAP) describes the definitions of analysis sets, derived variables, and statistical methods for all planned statistical analyses for protocol 56021927PCR2041.

| 1.1. | Objectives and E | ndpoints |
|------|------------------|----------|
|------|------------------|----------|

| Objectives | Endpoints |
|--|---|
| Primary | |
| • To assess if the combination of apalutamide and ADT in participants with high-risk localized prostate cancer improves the BCR-free rate. | • BCR-free rate at 24 months. BCR is defined as a confirmed PSA >0.2 ng/mL. |
| Secondary | |
| • To determine the BCR-free rate at 12 months. | • BCR-free rate at 12 months. |
| • To determine the time to serum testosterone recovery. | • Testosterone recovery rate at 18 and 24 months. |
| Exploratory | |
| • To evaluate the incidence of rash. | • Incidence of rash. |

Key: ADT=androgen-deprivation therapy; BCR=biochemical recurrence; PSA=prostate-specific antigen

1.2. Study Design

This is a single-arm, open-label, multi-center study of apalutamide and ADT in 96 participants with high risk localized prostate cancer who are treatment naïve, documented to have no evidence of metastatic disease prior to study entry, who are no more than 60 days post radical prostatectomy (RP), whose prostate-specific antigen (PSA) is ≤ 0.2 ng/mL at study entry and who have recovered from surgery, per the clinical judgement of the investigator.

There will be one intervention group receiving apalutamide with ADT of investigator's choice (3-month depot preferred) for 12 months. Treatment with apalutamide and ADT will start following screening and completion of RP and no later than postoperative Day 60. Approximately 30 days post-treatment, a safety follow-up examination will be completed (end of treatment visit). There will be a follow-up period during which serum PSA and testosterone levels will be measured and clinical status monitored every 6 months after the completion of treatment until the end of the study (EOS). The EOS is defined as the date of last participant's enrolment + 24 months or discontinuation of all study participants from the study, whichever occurs first. Study enrollment is defined as the day when the participant receives the first dose of apalutamide after having met all pre-screening criteria.

A diagram of the study design is provided below.

Key: ADT=androgen deprivation therapy; EOS=end of study; N=number of participants; post-op=postoperative; PSA=prostate-specific antigen; RP=radical prostatectomy.

2. STATISTICAL HYPOTHESES

The primary hypothesis of this study is that adjuvant treatment with apalutamide and ADT will improve the BCR-free rate at 24 months in the treatment-naïve, non-metastatic prostate cancer population who are at high risk for the development of metastases. The null hypothesis is that the BCR-free rate at 24 months is $\leq 76\%$.

3. SAMPLE SIZE DETERMINATION

It is assumed that BCR-free rate follows an exponential distribution with a constant hazard rate. It is estimated that approximately 94 participants accrued over approximately 1 year, treated for 12 months and followed for an additional 12 months would be required to provide at least 80% power in detecting a 10% absolute increase in BCR-free rate at 24 months of 76%¹ to 86% at a 1-tailed significance level of 0.05. Sample size was calculated using PASS 15 (Power Analysis and Sample Size Software $[2017]^2$.

4. POPULATIONS (ANALYSIS SETS) FOR ANALYSIS

Following analysis sets will be defined for analysis purposes.

- Safety Analysis Set: The safety analysis set will consist of all participants who received at least 1 dose of apalutamide. All safety analyses will be performed using the safety analysis set.
- Modified Intent-to-Treat Analysis Set: The Modified Intent-to-Treat set consist of all participants who satisfy all the following:
 - Met all eligibility criteria and are enrolled in the study

- Received at least 1 dose of apalutamide
- Had a baseline PSA and at least 1 post-treatment PSA assessment.

This analysis set will be used for efficacy analyses of endpoints and subject disposition, unless otherwise specified.

5. STATISTICAL ANALYSES

5.1. General Considerations

Study Day will be calculated in reference to the date of first dose of study drug (apalutamide). Positive study days will count forward from Study Day 1. Study Day -1 will be the day before Study Day 1, and all subsequent negative study days will be measured backward from Study Day -1. There will be no Study Day 0.

The first dose starts on Day 1 of Cycle 1.

Unless otherwise specified, baseline value is defined as the closest measurement prior to the first dose of study drug. Change from baseline will be defined as (post-baseline value – baseline value).

Treatment Duration will be calculated as the duration of time from the date of the first dose of study drug (apalutamide) to the date of last dose of the study drug, i.e., date of last dose – date of first dose + 1.

Time to Event endpoints will be calculated as the number of days from the start of the study drug to the date of the event of interest, i.e., date of event of interest – date of first dose + 1. Time to event or duration of event endpoints will be based on the actual date of the event, not visit number or visit label. Confidence intervals of survival function at specific time point will be calculated using Kaplan-Meier method. In case no events have occurred by the given time point, a conservative approach will be used by assuming one event at the time point among subjects still at risk.

Continuous/numerical variables will be summarized using mean, standard deviation (SD), median, minimum, and maximum. Categorical variables will be summarized using count and percentage. In general, means and other measures of central tendency will be displayed with one more decimal digit than collected, and standard deviations and other measures of variability will be displayed with two decimal digits more than collected. For frequency counts of categorical variables, categories for which the counts are zero will be displayed for the sake of completeness. For example, if no subject discontinued due to "withdrawal of consent", this reason would still be included in the table but with a count of 0.

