This is a single-arm, open-label, multi-center study of apalutamide and ADT in approximately 94 participants with high risk localized prostate cancer who are treatment naïve, documented to have no evidence of metastatic disease prior to study entry, who are between Day 29 and Day 90 post-RP, whose prostate-specific antigen (PSA) is ≤ 0.2 ng/mL at study entry and who have recovered from surgery, per the clinical judgment of the investigator. There will be one study intervention group receiving apalutamide for 12 cycles (a cycle is defined as 28 days); the participants will also receive an ADT of investigator's choice

(3-month depot preferred) for 12 months. Treatment with apalutamide and ADT will start following screening and completion of RP and no later than postoperative Day 90. Participants will receive 12 cycles of therapy. During treatment, participants should continuously be re-evaluated for emerging and worsening cardiovascular risk factors per current standards for patients under androgen deprivation. Approximately 30 days post-treatment, a safety follow-up examination will be completed (end of treatment visit). There will be a follow-up period during which serum PSA and testosterone levels will be measured and clinical status monitored every 6 months after the completion of treatment until the end of the study (EOS). The EOS is defined as the date of last participant's enrollment +24 months or discontinuation of all study participants from the study, whichever occurs first. Study enrollment is defined as the day when the participant receives the first dose of apalutamide after having met all prescreening criteria.

A Steering Committee will be commissioned for this study.

NUMBER OF PARTICIPANTS

This study will be conducted in approximately 30 urology practices in the United States and enroll approximately 94 participants. The sub-study consisting of 12 participants will be in addition to the 94 main ApaRP protocol and statistical analyses will be performed separately. Upon completion of the sub-study, participants will be transitioned into the main study beginning at Cycle 2 Day 1.

INTERVENTION GROUPS AND DURATION

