- a Beginning with Visits 2 through 8, a window of ±7 calendar days for scheduling will be allowed.
- b Beginning with Visit 9 and for all follow-up visits, a window of ±14 calendar days for scheduling will be allowed.
- c Must be signed before first study-related activity.
- d Provide 3-month supply of apalutamide during Visits 4, 5, and 6.
- e ADT first administration will be at baseline and subsequently administered per USPI for total duration 12 months, 3-month depot is the preferred administration. NOTE: If 3-month DEPOT is used, the last dose will be administered at Month 10. If 3-month DEPOT is not used, follow USPI.

- Clinical Protocol 56021927PCR2041 Amendment 2
- f A PSA level >0.2 ng/mL will be an indicator of BCR and will be confirmed within 3 to 4 weeks regardless of study visit and timing. Depending on timing, this may be captured as an unscheduled visit.
- g Focused examinations are generally limited to the body systems or regions based on participant's self-assessment and AE reporting. Any new complaints, symptoms reported by participants or adverse events noted by providers should guide the need and extent of physical examination.
- h ECG assessment at screening if not available from preoperative information.
- i Collected at baseline, 12 months or end of treatment, and at 24 months or progression (whichever comes first).
- j Tissue sample to be collected and sent to sponsor's laboratory partner along with a copy of the full histopathology report of the specimen. Biopsy tissue is preferred. See Section 8.6 for further details.
- k Collection of concomitant therapies does not begin until time of first dose of apalutamide.
- ^L Collection of AEs does not begin until time of first dose of apalutamide.

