4.4. End of Study Definition

End of Study Definition

The EOS is defined as the date of last participant's enrollment +24 months or discontinuation of all study participants from the study, whichever occurs first. The final data from the study site will be sent to the sponsor (or designee) after completion of the final participant visit at that study site, in the time frame specified in the Clinical Trial Agreement.

Study Completion Definition

Participants will be considered to have completed the study if they have completed EOS assessments.

Participants who prematurely discontinue study intervention for any reason before study completion will not be considered to have completed the study. If a participant misses a dose for >28 days, consult the sponsor regarding continuation in the study.

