6. STUDY INTERVENTION

6.1. Study Intervention Administered

The study intervention apalutamide, 240 mg (four 60 mg tablets, slightly yellowish to greyish green oblong film-coated tablets, debossed with "AR 60" on one side), will be provided as tablets for oral administration. The window for initiation of study intervention must occur between Day 29 and Day 90 post-RP. Participants will be instructed to take their assigned dose of the study intervention orally **once daily** for 12 cycles per ERLEADA USPI. A treatment cycle is defined as 28 days. Apalutamide can be taken with or without food. If a participant experiences a \geq Grade 3 toxicity or an intolerable side effect, hold dosing until symptoms improve to \leq Grade 1 or original grade, then resume at the same dose or a reduced dose (180 mg or 120 mg), if warranted. If a participant remains off apalutamide for \geq 4 weeks, the participant may be withdrawn from the study, after discussing with the sponsor. Participants experiencing treatment related seizure of any grade will have apalutamide permanently discontinued.

Description of Interventions

Study intervention administration must be captured in the source documents and the electronic case report form (eCRF). Study-site personnel will instruct participants on how to store study intervention for at-home use as indicated for this protocol.

Apalutamide will be manufactured and provided under the responsibility of the sponsor. Refer to the IB for a list of excipients and the ERLEADA USPI.

Investigator's choice of a Food and Drug Administration (FDA)-approved and commercially available ADT, not provided by the sponsor, will be administered per the USPI for 12 months in total duration, during the treatment phase. Three-month depot is the preferred administration. For further information on ADT refer to the USPI.

For a definition of study intervention overdose, refer to Section 6.7, Treatment of Overdose.

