5.6.1. Extent of Exposure

Treatment duration (in terms of cycles and in months) will be defined as the duration from the date of the first dose of study drug to the date of last dose of study drug. Descriptive summary

statistics for duration of apalutamide treatment (N, mean, SD, median, and range (minimum, maximum)) will be summarized using safety analysis set.

Treatment duration will be calculated as the number of days with dosing record divided by 28 (i.e., expected number of days in a cycle) and 30.4375 (i.e., number of days in a month calculated as 365.25/12).

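### The PSA visit behind the 24-month primary endpoint carries two conflicting times, and on two of three readings the type I error of the 76% test rises well above 5%

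*SAP*

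**What the plan says.** **Protocol 1.3 (Schedule of Activities).** One column, Visit 10, is headed both C24/D1 and Month 24. Baseline is headed both C1/D1 and Month 1. The next PSA is Visit 11 (C30/D1, Month 30). Footnote b reads: "Beginning with Visit 9 and for all follow-up visits, a window of ±14 calendar days for scheduling will be allowed". Footnote f adds an extra PSA only to confirm a value already above 0.2 ng/mL, within 3 to 4 weeks.

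**Protocol 6.1.** "A treatment cycle is defined as 28 days". Twelve cycles are given.

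**Protocol 1.1 and 4.1.** The follow-up text describes six-monthly checks once treatment has ended.

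**Protocol 4.4.** "The EOS is defined as the date of last participant's enrollment +24 months", or discontinuation of all participants if that comes first.

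**SAP 5.1.** Time to event is "the number of days from the start of the study drug to the date of the event of interest", plus 1. It continues: "Time to event or duration of event endpoints will be based on the actual date of the event, not visit number or visit label".

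**SAP 5.3.3.** The null is rejected if the lower 90% limit of the Kaplan-Meier BCR-free rate at 24 months exceeds 76%. Men without confirmed recurrence are censored at their last PSA.

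**SAP 5.6.1.** The month length is given as "number of days in a month calculated as 365.25/12", which is 30.4375 days.

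**The concern.** A recurrence is known only when a PSA is drawn, and it is dated on the day of that draw. The curve at 24 months therefore reflects whatever the last scheduled PSA on or before day 730.5 has found.

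If Visit 10 is earlier than that, recurrences between the visit and the landmark are not counted. If Visit 10 is centred on the landmark, recurrences found in the second half of its window are dated too late to count. Both push the estimate up against a fixed 76%. In a single-arm trial that comparison is the whole confirmatory inference, so the size of the test depends on which header row a site follows.

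**Working it through.** **Inputs.** From SAP 3: 94 participants, accrual over about 1 year, null 76%, alternative 86%, one-sided 0.05, power at least 80%, exponential times. From SAP 5.3.3: the 90% lower-limit rule and censoring at last PSA. From Protocol 1.3: windows of ±7 days for Visits 2 to 8 and ±14 days from Visit 9. Assumptions not in the documents: visits scatter evenly over the window, accrual is uniform, and dropout is zero (10% as a check). The interval is taken as plain or log-log, because the SAP names no transformation.

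**The plan's own figure.** The one-sample arcsine formula gives N = [(1.645 + 0.842) / (2(asin√0.86 − asin√0.76))]² = 93.6, so 94, with power 80.1%. The stated size reproduces if status is known at 24 months.

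**Benchmark for the actual rule.** With complete 24-month observation, rejection needs 78 of 94 men BCR-free (plain) or 79 (log-log). Exact type I error is 6.8% / 4.0%, and power is 84% / 76%.

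**When is Visit 10?**
- Cycle label: 23 × 28 + 1 = day 645; 645 / 30.4375 = 21.2 months. The window is days 631 to 659.
- Month label with baseline as Month 1: 23 × 30.4375 + 1 = about day 701.
- Month label taken nominally: 24 × 30.4375 = day 730.5.
- Follow-up text: Visit 7 to Visit 9 is 5 × 28 = 140 days by cycle, or 5 months by month label. Neither is six months, so the text does not settle the matter.

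**Reading 1, day 645.** Visit 11 is at 29 × 28 + 1 = day 813, no earlier than day 799. No PSA is scheduled between days 659 and 799. The curve at 24 months then estimates 0.76^(21.19/24) = 0.785 under the null and 0.86^(21.19/24) = 0.875 under the alternative. With every visit on day 645, exact type I error is 17.5% / 11.5%. Placing the null by the historical 84% and 76% at 12 and 24 months (Protocol 4.2) gives 0.778 and 13.8% / 8.8%.

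**Reading 3, day 730.5 ±14.** If Visit 9 is at 18 months, the null recurrences Visit 10 can find are 0.76^(18/24) − 0.76 = 0.814 − 0.760 = 0.054. If half are dated after the landmark, the estimate is near 0.760 + 0.027 = 0.787. Simulation gives a mean of 0.785.

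**Simulation with windows, accrual and end-of-study cut-off** (plain / log-log; ranges are across separate runs):

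| Visit 10 at | Type I error | Power |
|---|---|---|
| Day 645 | 13-15% / 9-10% | about 90% / 85% |
| About day 701 | 5-6% / 3% | about 78% / 69% |
| Day 730.5 ±14 | 17-20% / 11-13% | about 92% / 88% |

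With 10% dropout the day-645 figures are 12.9% / 8.1% type I error and 88% / 81% power.

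The day-701 result is near nominal partly because two errors offset. Missing the last month raises the null estimate to 0.768. Window scatter lowers the mean to about 0.754, because late enrollees with a clear PSA early in the window are censored before recurrences found later in it. Without scatter, type I error is 9.6% / 5.8% and power 87% / 80%.

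**Effect of assigning Visit 10 to the nominal 24-month day.** If the visit truly is at 24 months: about 7% / 4% type I error and 84% / 77% power, which matches the benchmark. If it was really on day 645, relabelling gives about 18% / 12%. If on day 701, about 10% / 6%.

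**The case against.** A reader might infer that the visit simply is on day 645. The documents do not say so. The 28-day definition is of a treatment cycle, only 12 are given, and Visits 9 to 12 are off treatment. The six-monthly text and the sample-size wording (12 months treated, 12 more followed) point nearer to 23 or 24 months. What stands is that the column carries both labels and nothing ranks them.

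A reader might also infer that both error rates fail on every reading. They do not. At day 645 power stays above 80% and only type I error moves. At 23 months with a plain interval both are close to plan. Even complete observation does not give exactly 5% and 80% under this rule.

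Nor is the SAP's actual-date sentence a mistake in itself. It is an ordinary convention that does harm only when combined with this schedule.

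The end-of-study date might seem to leave no room for confirmation. At day 645 about 85 days remain. The squeeze arises only if Visit 10 is near 24 months, and then for men enrolled in roughly the last 14 + 28 = 42 days of a one-year accrual (42/365 = 12%). The planned sensitivity analysis of unconfirmed recurrence partly covers them.

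Counting from surgery does not rescue the test. C24/D1 is 29 + 644 = 673 to 90 + 644 = 734 days after surgery (22.1 to 24.1 months), but the SAP's clock starts at first dose and entry requires PSA ≤0.2 ng/mL. Under a constant hazard the 0.785 is unchanged.

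One limit remains: the documents do not say how often PSA was measured in the historical cohort, so any detection lag within the 76% is not allowed for.

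**Conclusion.** The defect is an unreconciled visit time that the SAP's landmark reading makes consequential. Against a stated 5%, type I error is about 13-15% / 9-10% if sites follow the cycle label, and about 17-20% / 11-13% if they aim at 24 elapsed months. At 23 months it is about 5-6% / 3%, at the cost of power (about 78% / 69%). These figures rest on exponential times, no dropout, even scatter within windows and uniform accrual; dropout or the 84%/76% historical curve makes the day-645 inflation smaller but does not remove it. The stronger claim, that the test fails its size and its power whichever way the schedule is read, is not supported.

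**What to change.** 1. In Protocol 1.3, replace the paired cycle and month labels for Visits 9 to 12 with one study-day number each, counted from first dose, with Visit 10 at 24 elapsed months.
2. In SAP 5.3.3, assign Visit 10 PSA results obtained within the window to the nominal 24-month day, for recurrent and non-recurrent men alike, so that everyone seen at that visit counts at the landmark. Name the confidence-interval transformation in the same place.
3. Let the end of study cover the last participant's Visit 10 window plus the 3 to 4 week confirmation. This matters for late enrollees only.
4. If visits have already taken place near day 645 or day 701, do not relabel them as 24 months, since that raises type I error and no wording can recover a PSA that was not drawn. Restate the landmark as the time actually observed and set the historical comparator at that same time.
5. Apply the same correction to the 18-month testosterone estimate: C18/D1 is 17 × 28 = 476 days after first dose, or 476 / 30.4375 = 15.6 months.

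The cost is SAP and schedule wording, and up to about 6 weeks' later close-out (14 + 28 = 42 days).

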5.1.1. Visit Windows

The reference day is Cycle 1 Day 1 of the treatment. A visit window of ± 7 calendar days for visits 2 through 8 and a visit window of ± 14 calendar days for visit 9 onwards for all follow-up visits are set up for this study.

5.2. Participant Dispositions

The number of participants in the following disposition categories will be summarized during treatment period using safety analysis set:

- Participants enrolled
- Participants who received study treatment
- Participants who completed the study
- Participants who discontinued study treatment
- Reasons for discontinuation of study treatment
- Participants who terminated study prematurely
- Reasons for termination of study

A listing of participants will be provided for the following categories:

- Participants who discontinued study treatment
- Participants who terminated study prematurely

5.3. Primary Endpoint(s) Analysis

The primary endpoint of the study is BCR-free rate at 24 months. BCR is defined as a confirmed PSA > 0.2 ng/mL.

BCR-free rate will be estimated from primary efficacy variable (time to BCR) using Kaplan-Meier method in modified intent-to-treat analysis set.

5.3.1. Definition of Endpoint(s)

Time to confirmed BCR will be defined as the time between the date of the first dose of study drug (apalutamide) and the date of the first occurrence of confirmed PSA > 0.2 ng/mL. Confirmation of PSA value will be done within 3-4 weeks regardless of study visit and timing. Depending on timing, this may be captured as an unscheduled visit.

Subjects without confirmed PSA > 0.2 ng/mL (including subjects who are lost-to-follow up) will be censored on their last PSA date during treatment phase of the study. Additional censoring rules are provided in 5.3.3.

The time to unconfirmed BCR (from the first dose of the study drug to the first occurrence of PSA > 0.2 ng/mL) will be used for sensitivity analysis of the primary endpoint using similar methodology.

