5.3.2. Estimand

The primary estimand, the main clinical quantity of interest to be estimated in the study, is defined by the following 4 components -

5.3.2.1. Population:

Subjects with high-risk localized or locally advanced prostate cancer who are treatment-naïve and have undergone RP for non-metastatic prostate cancer with post RP PSA ≤ 0.2 ng/mL

5.3.2.2. Variables:

• Time to confirmed BCR (confirmed PSA > 0.2 ng/mL).

5.3.2.3. Intercurrent Events and Strategies:

Table 1

| Intercurrent Events (IE) | Strategy for Addressing IE | Description of Strategy | Data to be Included |
|---|------------------------------------|---|--|
| Treatment discontinuation during treatment phase but continuing in the study. | Treatment Policy strategy | Occurrence of the IE is considered irrelevant in defining the treatment effect of interest | PSA value at the time of the primary analysis |
| Study withdrawal due to any reason, any time during the study (including treatment & study discontinuation during treatment phase) | While-on- Treatment strategy | Response to treatment prior to the occurrence of the IE is of interest | PSA value at the time of study withdrawal |
| Use of restricted and prohibited concomitant therapy any time during the study | While-on- Treatment strategy | Response to treatment prior to the occurrence of the IE is of interest | PSA value at the time of the start of restricted and prohibited concomitant therapy |
| Other protocol deviations | Treatment Policy strategy | Occurrence of the IE is considered irrelevant in defining the treatment effect of interest | PSA value at the time of the primary analysis |
| Death | While-Alive strategy | Response to treatment prior to the occurrence of the IE is of interest | PSA value at the time of death |

5.3.2.4. Population level summary:

Time to confirmed BCR endpoint: Kaplan-Meier method will be used to estimate BCR-free rate at primary time point (24 months) along with 95% confidence interval.

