5.3.3. Analysis Methods

The analysis of time to BCR will be performed at the end of study which is defined as the date of last participant's enrolment + 24 months or discontinuation of all study participants from the study, whichever occurs first. The distribution of time to BCR will be estimated using the Kaplan-Meier (KM) method. Median BCR-free time along with 90% confidence interval will be reported with Kaplan-Meier curve. The null hypothesis will be rejected if lower limit of the 90% confidence interval of KM estimate of BCR-free rate at 24 months is > 76%.

Time to unconfirmed BCR will be evaluated using same methodology as sensitivity analysis.

Modified ITT analysis set will be used for the analysis. Subjects with no evidence of BCR will be censored based on following rule:

- If the subject does not have baseline PSA measurement, the subject will be censored on the date of enrollment (Study Day 1)
- If the subject does not have confirmed PSA >= 0.2 ng/mL, the subject will be censored on the date of the last PSA measurement
- If the subject receives a protocol specified prohibited or restricted therapy, PSA measurements on or after such therapy will not be included in the analysis

These censoring rules will be applied appropriately to all intercurrent events in the trial as defined in Table 1. The details are as specified in Table 2.

| Intercurrent Event (IE) / EOS | Censoring (if no event, before the IE) | Assumption |
|--|---|---|
| IE: Study withdrawal due to any reason, any time during the study | PSA value censored at study withdrawal | Non-informative censoring as per censoring rule |
| IE: Use of restricted and prohibited concomitant therapy any time during the study | PSA value censored at the last PSA assessment prior to the time of the start of restricted and prohibited concomitant therapy | Non-informative censoring as per censoring rule |

Table 2: Censoring Rules to be used for intercurrent events

| IE: Death | PSA value censored at the last PSA assessment prior to the time of death | Non-informative censoring as per censoring rule |
|--------------|--|---|
| End of study | (Administratively) censored at the last PSA assessment prior to the end of the study | Non-informative censoring as per censoring rule |

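### SAP 5.3.1 censors recurrence-free men at the end of treatment; this contradicts SAP 5.3.3 and protocol 9.4.2 and, applied literally, destroys the 24-month primary estimate

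*SAP*

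**What the plan says.** SAP 5.3.1 defines the event date as "the date of the first occurrence of confirmed PSA > 0.2 ng/mL", with no limit to any phase of the study. Participants without such an event, including those lost to follow-up, "will be censored on their last PSA date during treatment phase of the study". The section then adds: "Additional censoring rules are provided in 5.3.3".

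Other places give the same participants a different date:

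- SAP 5.3.3, second bullet: "If the subject does not have confirmed PSA >= 0.2 ng/mL, the subject will be censored on the date of the last PSA measurement".
- SAP Table 2, End of study row: "censored at the last PSA assessment prior to the end of the study".
- SAP Table 1, treatment-policy rows: the data to be used are the "PSA value at the time of the primary analysis", so PSA after stopping treatment counts.
- Protocol 9.4.2: censoring at the last PSA measurement, with no phase limit.

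On timing, SAP 5.3.3 states: "The analysis of time to BCR will be performed at the end of study". SAP 5.4.1 refers to 5.3.3 as the censoring rule of the primary analysis. SAP Appendix 2 lists no departure from the protocol that would explain 5.3.1.

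**The concern.** A Kaplan-Meier estimate at 24 months needs recurrence-free men to be followed to 24 months. SAP 5.3.1 removes all of them when treatment ends, although the Schedule of Activities collects PSA through the follow-up visits.

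Because events are not limited by phase, the literal rule makes censoring depend on the future outcome. A man who will recur in follow-up stays at risk until he does; a man who will not is removed at about one year. Every row of Table 2 assumes non-informative censoring, and this rule violates that by construction.

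The trial has one hypothesis test: reject if the lower 90% limit of the 24-month estimate exceeds 76%. The censoring rule feeds it directly. The literal error runs against the treatment. There is also a possible misreading in the other direction: if an analyst dropped follow-up recurrences as well and carried the curve forward, the rate at about 12 to 14 months would stand in for the 24-month rate.

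**Working it through.** **Inputs.** From protocol 9.2 and SAP 3: 94 participants, about 1 year of accrual, exponential times, 76% against 86% at 24 months, one-sided 0.05. From the protocol: 12 cycles of 28 days, PSA visits as in the Schedule of Activities, end of study at last enrolment + 24 months. From SAP 5.6.1: 30.4375 days per month, so 24 months = 730.5 days.

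**The plan's own figure.** A one-sample arcsine calculation reproduces it: n = [(1.645 + 0.842) / (2(asin√0.86 − asin√0.76))]² = 93.64, rounded up to 94, with power 80.1%. The sample size is not in dispute.

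**Where 5.3.1 censors.** The SAP gives no treatment-phase boundary for efficacy, so three visit timings were used, each with the cut at V7 (labelled end of treatment) or V8 (safety visit):

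| Timing | V7 | V8 | Month 24 visit |
|---|---|---|---|
| (i) 28-day cycles | 12×28+1 = 337 | 13×28+1 = 365 | 23×28+1 = 645 |
| (ii) calendar months, Month 1 = Day 1 | 366 | 397 | 701 |
| (iii) calendar months elapsed | 396 | 426 | 730.5 |

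The shortest gap to the read point is 730.5 − 426 = 304.5 days. Men who stop treatment early could be censored sooner still.

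**Expected counts at a true 86%.** S(12 months) = √0.86 = 0.927. Expected recurrences are 94 × (1 − 0.927) = 6.8 in months 0–12 and 94 × (0.927 − 0.86) = 6.3 in months 12–24. About 94 × 0.86 = 81 men are recurrence-free at 24 months, and the literal rule has censored all of them by then.

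**Why the curve collapses.** Just after the cut the simulated risk set is 6.7–8.4 men, all future recurrences. With no further censoring among them, the estimate is S(cut) × (number left at 24 months ÷ number at the cut). Taking S(337 days) = 0.933 and 8 men at the cut, timing (i) with 3.2 men left gives 0.933 × 3.2/8 = 0.37, and timing (ii) with 2.1 left gives 0.933 × 2.1/8 = 0.24.

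**Simulation.** 4,000 runs per cell, uniform accrual, no dropout, BCR dated at the first PSA visit after onset. Plain and log-log 90% intervals were both run because the SAP names no transformation. Ranges cover the three timings, both cuts and both intervals.

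| Rule | True rate | Mean 24-month estimate | Null rejected |
|---|---|---|---|
| Literal 5.3.1 | 86% | 0.19–0.35 | 0.2–0.7% |
| 5.3.3 / Table 2 | 86% | 0.86–0.88 | 78–93% |
| Literal 5.3.1 | 76% | 0.16–0.32 | at most 0.03% |
| 5.3.3 / Table 2 | 76% | 0.76–0.79 | 3.6–17.4% |
| Misreading (follow-up BCRs dropped) | 76% | – | 69–95% |

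The misreading row follows from S(337 days) = 0.881 and S(14 months) = 0.852 at a true 76%: both lie well above the 76% threshold.

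**Sensitivity of the literal rule at 86%** (1,500 runs per cell):

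- Visits spread over the ±7 and ±14-day windows: mean 0.23–0.41, rejected in at most 1.5%.
- 10% dropout by month 24 (assumed): mean 0.19–0.34, at most 0.9%.
- Timing (iii) with the Month 24 visit one day after the read point: mean 0.58–0.62, 6–11%. The 5.3.3 rule there gives 0.89 and 96–98%.

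A separately coded simulation (2,000 runs, log-log) gave 0.18–0.36 and at most 0.6% for the literal rule at 86%. Even at a true 95% its literal mean was only 0.24–0.42.

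**The case against.** The strongest reply is that nobody would run the literal rule. SAP 5.3.3 is the analysis-methods section, 5.4.1 names it as the primary censoring rule, Table 2 has an explicit end-of-study row, and the protocol agrees. A curve resting on a handful of men would be noticed. This is fair as to intent: 5.3.1 is very probably a drafting error, and the collapsed estimate is a conditional result, not a forecast. But no text withdraws the sentence, and it sits in the endpoint definition. Resolving it once the curve looks wrong would mean choosing the primary censoring rule with open-label, single-arm results in view.

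Three narrower points have some force:

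- SAP 5.1 adds one day to every event time. Under that formula, timing (iii) puts the Month 24 visit just after 730.5 days, so the 0.58–0.62 case is the SAP-consistent version of that timing and belongs beside the main figures. The literal rule still fails there.
- Day 337 to 426 is derived, and Day 426 needs Month 14 read as 14 elapsed months. No cut tried changes the conclusion.
- The sentence "Confirmation of PSA value will be done within 3-4 weeks regardless of study visit and timing" concerns when the confirmatory sample is drawn, so it is weak evidence that follow-up recurrences count. The event definition itself carries that reading.

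The 5.3.3 rule's own rejection rate above 5% at a true 76% under some timings is not caused by 5.3.1.

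**Conclusion.** The concern holds. SAP 5.3.1 as written contradicts SAP 5.3.3, Tables 1 and 2 and protocol 9.4.2 on the censoring date for the primary endpoint. Read literally, it gives a mean 24-month estimate between 0.19 and 0.62 when the true rate is 86%, and rejects the null in at most about 11% of runs (up to 13% in a repeat simulation of the most favourable timing). The contradiction itself rests on the text alone. The sizes rest on exponential recurrence, 94 men, an assumed mapping of visit labels to days, and no dropout in the main settings. They vary with visit timing, but the literal rule fails in every setting tried. Because it governs the only hypothesis test, it must be corrected.

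**What to change.** In SAP 5.3.1, replace the restriction to the treatment phase so that the sentence censors on *the date of the last on-study PSA measurement (treatment or follow-up phase), subject to the intercurrent-event rules in Section 5.3.3 and Table 2*.

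Correct the phrase itself; do not simply declare 5.3.3 governing. The first bullet of 5.3.3, for men with no baseline PSA, cannot apply in a modified ITT set that requires one (SAP 4).

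Two optional alignments fit in the same edit: change the threshold in the second bullet of 5.3.3 from ≥ 0.2 to > 0.2 ng/mL to match the endpoint, and word the study-withdrawal row of Table 2 as the last PSA assessment before withdrawal.

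The cost is one phrase in the SAP, with no new data and no protocol amendment. It should be made before database lock; the documents give no lock date.
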